### **7.5.2.2 Subgroup Analyses**

OS will be summarized within subsets defined by information recorded on the baseline CRF (with two-sided 80% CI for the median OS calculated via the method of Brookmeyer and Crowley). For informal comparisons of OS within these subsets, the HR, and its 80% two-sided CI, of ipilimumab

to DTIC will be computed using an unstratified Cox proportional hazards model with treatment as the single covariate.

This summary and comparison will be provided for the following subgroups:

- by age (< 65,  $\geq$  65)
- by gender (male, female)
- by M-Substage at study entry (M1a/M1b, M1c)
- by ECOG performance status (0, 1)
- by baseline LDH ( $\leq$  ULN,  $>$  ULN)
- by baseline LDH ( $\leq 2 \times$  ULN,  $> 2 \times$  ULN)
- by BRAF mutation status (positive, negative, unknown)
- by subtype (acral, cutaneous, other)

In case a subgroup includes less than 10 subjects, the analysis for the given subgroup will not be carried out (or the possibility of combining subgroups will be considered).

### **7.5.2.3 Sensitivity Analyses**

An unstratified log-rank test will be performed to compare OS between treatment groups. The HR of ipilimumab to DTIC and the corresponding two-sided 80% CI will also be estimated using an *unstratified*, multivariate Cox proportional hazards model, with covariates for stratification factors (from CRF), as well as for treatment group.

- Comparison of OS using unstratified log-rank test
- Comparison of OS using multivariate Cox model
- Furthermore, the following analyses will be presented for the modified OS (defined in [Section 4.2.2](#)):
  - Summary of OS accounting for subsequent PD-1/PD-L1 therapy
  - Comparison of OS accounting for subsequent PD-1/PD-L1 therapy
  - KM plot of OS accounting for subsequent PD-1/PD-L1 therapy

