**Figure 2.1-1: Study Design Schematic**

### 2.2 Treatment Assignment

After informed consent has been obtained, the site will enroll a subject into the study at the time of eligibility screening by accessing a call-in Interactive Voice Response System (IVRS). A subject number will be assigned by the IVRS at this time.

Following completion of all Screening evaluations, all eligible subjects will be randomized to one of two arms in a 2:1 ratio (Ipilimumab:DTIC) using a stratified permuted block randomization method with the following stratification actors:

- M-substage (M1a+M1b vs. M1c);
- BRAF mutation status (yes vs. no).

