## 5 SAMPLE SIZE AND POWER

Approximately 180 Chinese subjects will be randomized to ipilimumab and DTIC at a 2:1 ratio and followed at least 2 years after randomization to ensure 80% power through simulation using a chi-squared test with a Type I error rate of 0.20 to reject the null hypothesis of no difference in 2-year survival rate between treatment groups, assuming a HR [ipilimumab vs DTIC] of 0.67. Under an exponential distribution, this hazard ratio (HR) would correspond to an 12 month median OS for the ipilimumab arm with an 8 month median OS in the DTIC arm^8(or equivalently 25% and 12.5% in the ipilimumab and DTIC arm). The accrual duration is approximately 18 months, assuming a monthly rate of 10 subjects per month. The primary analysis will be performed about 42 months after the first subject is randomized.

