## **7.5 Efficacy**

All hypothesis testing will be two-sided and will be based upon a significance level of 0.20.

No type I error rate multiplicity adjustment will be made for secondary endpoint testing. P-values associated with the comparisons of OS, DCR and PFS will be purely descriptive in nature. All efficacy analyses will be based on all randomized subjects, as randomized, unless indicated.

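### The multivariate Cox sensitivity models for OS and PFS leave out baseline LDH, so no overall LDH-adjusted hazard ratio is planned; adding it is a free, low-severity improvement.

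*SAP*

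**What the plan says.** SAP 2.2 stratifies randomisation by M-substage (M1a and M1b together against M1c) and by "BRAF mutation status (yes vs. no"). LDH is not a stratification factor.

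Baseline LDH is nevertheless collected. SAP 7.3.2 tabulates it at ULN and at 2 x ULN, and SAP 7.1 makes such tables by treatment group. Both cut-offs define subgroups for 2-year survival (7.5.1.1) and for OS, where 7.5.2.2 lists results "by baseline LDH". Each OS subgroup model has treatment as its only covariate. No LDH subgroups are listed for PFS.

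The main Cox models for OS (7.5.2.1) and PFS (7.5.3) are stratified by the IVRS values of the two stratification factors. The sensitivity analyses in 7.5.2.3 and 7.5.3.1 each add an unstratified "multivariate Cox proportional hazards model, with covariates for stratification factors (from CRF), as well as for treatment group". No section plans an overall treatment effect adjusted for LDH or ECOG status.

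SAP 7.5 states: "All hypothesis testing will be two-sided and will be based upon a significance level of 0.20". The same section gives the OS, DCR and PFS p-values descriptive status only. The primary endpoint is the 2-year survival rate, tested by a stratified chi-square on Kaplan-Meier estimates (7.5.1).

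**The concern.** The SAP treats LDH as relevant enough to survival to split on it twice. Yet the adjusted models bring in no baseline factor beyond the two that the main models already stratify by. They can show whether the result depends on how those two factors are recorded or modelled. They cannot show whether it depends on a prognostic factor left to chance.

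If LDH is prognostic and happens to be unevenly distributed, both the main and the adjusted hazard ratio carry that imbalance. The baseline table would reveal it but would not say how far it moved the estimate. An adjustment chosen after seeing that table in an open-label trial is open to the criticism that pre-specification avoids. OS is named the key secondary endpoint, so its hazard ratio will be read closely even though its p-value is descriptive.

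**Working it through.** **Inputs from SAP 5.** "Approximately 180 Chinese subjects will be randomized to ipilimumab and DTIC at a 2:1 ratio", taken as 120 and 60; "80% power through simulation using a chi-squared test with a Type I error rate of 0.20"; "assuming a HR [ipilimumab vs DTIC] of 0.67"; "12 month median OS for the ipilimumab arm with an 8 month median OS in the DTIC arm"; 2-year survival of 25% and 12.5%; accrual over 18 months; analysis at about 42 months, so 24 to 42 months of follow-up each. The protocol's 258 (section 3.1) counts enrolled subjects and is not used.

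**Assumed, because the documents give no figures.** Share with elevated LDH 20-50%; LDH hazard ratio 1.5-2.5.

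**1. The plan's own figure.** The SAP statistic divides the difference in 2-year survival by its Greenwood variance. With every subject followed for 24 months this equals the unpooled binomial variance. Ignoring strata:

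- SE = sqrt(0.25 x 0.75/120 + 0.125 x 0.875/60) = 0.0582
- power = Phi(0.125/0.0582 - 1.282) = 0.807

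Simulation (400,000 runs) gives 0.800, so the stated 80% reproduces. The fix does not touch it.

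**2. Precision of the OS hazard ratio.** Exponential survival with this follow-up gives about 158 deaths (157.5 unrounded). SE(log HR) = 1/sqrt(157.5 x 2/3 x 1/3) = 0.169. The 80% CI half-width is 1.282 x 0.169 = 0.217, a factor of about 1.24 either way.

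**3. How often LDH is unbalanced.** SD of the difference in elevated share = sqrt(p(1-p)(1/120 + 1/60)).

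| Share elevated | SD (points) | P(gap > 10 points) | P(gap > 15 points) |
|---|---|---|---|
| 20% | 6.3 | 11% | 2% |
| 30% | 7.2 | 17% | 4% |
| 40% | 7.7 | 20% | 5% |
| 50% | 7.9 | 21% | 6% |

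**4. What such a gap does.** 4,000 simulated trials per row, true treatment HR 0.67, LDH independent of other factors. The models contain treatment alone, or treatment plus LDH. Each pair reads without LDH / with LDH.

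| Share, LDH HR | All trials | >10 points commoner on ipilimumab (ratio) | >10 points commoner on DTIC (ratio) | Power at 0.20, % |
|---|---|---|---|---|
| 30%, 1.5 | 0.674 / 0.667 | 0.715 / 0.672 (1.064) | 0.635 / 0.663 (0.958) | 85.4 / 86.4 |
| 30%, 2.0 | 0.682 / 0.665 | 0.743 / 0.667 (1.114) | 0.633 / 0.669 (0.946) | 83.6 / 86.6 |
| 40%, 2.0 | 0.692 / 0.671 | 0.754 / 0.675 (1.117) | 0.631 / 0.670 (0.942) | 80.8 / 85.5 |
| 30%, 2.5 | 0.694 / 0.666 | 0.774 / 0.670 (1.155) | 0.624 / 0.669 (0.933) | 79.7 / 85.1 |

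The shift is about 4-15%. It is larger upwards because leaving out a prognostic covariate also pulls the hazard ratio slightly towards 1, as the all-trials column shows.

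**5. Type I error.** With a true HR of 1 and no LDH in the model, rejection at 0.20 is 0.191-0.199. With LDH it is 0.196-0.218.

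**6. If LDH tracks M-substage.** As an extreme case, let elevated LDH occur only in M1c (half of M1c subjects; M1c 50-70% of the trial; M1c HR 1.3). Balance randomisation on M-substage and keep M-substage in both models. With 1,500 trials per setting, gaps above 10 points fall to 6-14% of trials. Each 10 points still moves the log HR by about 0.04-0.09. Imbalance becomes rarer; its effect when it occurs is similar.

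Nothing was computed for PFS or for ECOG status.

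**The case against.** The strongest reply is that nothing here is invalid. Randomisation justifies the comparison, and adjusting only for stratification factors is a coherent pre-specified choice. The sensitivity model is not a repeat of the main one either: it replaces IVRS strata with CRF covariates and so tests recording errors and model form. All of that stands.

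It also stands that LDH is used for OS. A hazard ratio within an LDH subset is free of imbalance across that cut-off, and the baseline table would show the imbalance. What remains missing is one pooled adjusted estimate, and for PFS any LDH analysis at all.

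A reader might infer that a modest imbalance could carry the trial across its decision line. The documents do not support that. The OS and PFS p-values are descriptive, and the primary test is a different analysis. Even against the nominal 0.20 level the distance is large. Take 0.083 on the log scale per 10 points, the largest value in a separate simulation with LDH elevated in 30-50% and the same range of LDH effects. Moving the planned effect of 0.40 to the threshold of 0.217 then needs (0.40 - 0.217)/0.0083, or about 22 points. That is about 2.8 SD at 50% prevalence.

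Finally, the size rests on LDH figures that the documents do not give, and the main simulation leaves M-substage and BRAF out of both models. The extreme case in step 6 answers this in part: the point shrinks but does not vanish.

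**Conclusion.** The point holds as a modest improvement to two sensitivity analyses, not as an error in the plan. The adjusted OS and PFS hazard ratios would carry a chance LDH imbalance that the trial has the data to remove.

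Under the assumed prevalence, a gap above 10 points occurs in about 11-21% of trials. It shifts the hazard ratio by about 4-15% under the assumed LDH effect, simulated at 30-40% elevated. That is smaller than the sampling error, whose 80% limits span a factor of 1.24 either way. Adjustment also recovers about 1 to 5 points of power at the nominal 0.20 level when LDH is independent of M-substage. The overall effect is smaller if the two are related.

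The primary test, the sample size and type I error averaged over randomisations are unaffected. Severity is low.

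**What to change.** In SAP 7.5.2.3 and 7.5.3.1, add baseline LDH to the multivariate Cox models beside treatment, M-substage and BRAF status. Use one cut-off stated in advance, for example at or below ULN against above ULN. ECOG status (0 against 1) may be added as an option; it is already a survival subgroup factor. Keep subjects with missing LDH in a category of their own so that all randomised subjects stay in the model. Leave the primary test and the main stratified Cox models as they are.

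The cost is one line of SAP text and one or two covariates in models already planned. No new data are needed.

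Protocol 5.4.1 and 5.4.2 give the database lock as 03 June 2019. If the SAP can no longer change, report the LDH-adjusted hazard ratios as supplementary and label them as not pre-specified.

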### **7.5.3 Progression-Free Survival**

PFS is one of the secondary endpoints. Similar methods as defined for OS will be used for PFS.

PFS within treatment group, estimated using the KM product-limit method, will be plotted. The plot will display the median PFS, together with a two-sided 80% CI for the median, calculated using the method of Brookmeyer and Crowley.

For the comparison of PFS between the treatment groups, a two-sided log-rank test, stratified by M substage (M1a+M1b versus M1c) and BRAF mutation status (yes vs no), as recorded in the IVRS, will be used.

The HR, and its two-sided 80% CI, of ipilimumab to DTIC will be estimated using a Cox proportional hazards model, stratified by the factors described above, and with treatment as the single covariate.

- Summary of PFS
- Comparison of PFS

#### **7.5.3.1 Sensitivity Analyses**

An unstratified log-rank test will be performed to compare PFS between treatment groups. The HR of ipilimumab to DTIC and the corresponding two-sided 80% CI will also be estimated using an *unstratified*, multivariate Cox proportional hazards model, with covariates for stratification factors (from CRF), as well as for treatment group.

- Comparison of PFS using unstratified log-rank test
- Comparison of PFS using multivariate Cox model
- Furthermore, the following analyses will be presented for the modified PFS variables (defined in [Section 4.2.3](#)):
  - Summary of PFS accounting for early TAs in DTIC group
  - Comparison of PFS accounting for early TAs in DTIC group
  - KM plot of PFS accounting for early TAs in DTIC group

#### **7.5.4 Disease Control Rate**

Exact, two-sided 80% CI for DCR within treatment group will be calculated using the method of Clopper and Pearson.

For the comparison of DCR between treatment groups, a Cochran-Mantel-Haenszel (CMH) test with an associated odds ratio estimate and exact two-sided 80% CI, stratified by M substage (M1a+M1b versus M1c) and BRAF mutation status (yes vs. no), as recorded in the IVRS, will be applied.

- Summary of DCR (primary definition)
- Comparison of DCR (primary definition)
- Summary of DCR (per protocol definition)
- Comparison of DCR (per protocol definition)

#### **7.5.5 Best Overall Response**

- Summary of BOR (primary definition)
- Summary of BOR (per protocol definition)

#### **7.5.6 Best Overall Response Rate**

An exact, two-sided 80% CI for BORR within treatment group will be calculated using the method of Clopper and Pearson.

- Summary of BORR (primary definition)
- Summary of BORR (per protocol definition)

### **7.5.7 Duration of Response**

The DoR in subjects with a BOR of CR or PR, estimated using the KM product-limit method, will be plotted. The plot will display the median duration, together with a two-sided 80% CI for the median, calculated using the method of Brookmeyer and Crowley.

- Summary of DoR (primary definition)
- Summary of DoR (per protocol definition)

### **7.5.8 Duration of Stable Disease**

The DoSD in subjects whose BOR is SD, estimated using the KM product-limit method, will be plotted. The plot will display the median duration, together with a two-sided 80% CI for the median, calculated using the method of Brookmeyer and Crowley.

- Summary of DoSD (primary definition)
- Summary of DoSD (per protocol definition)

## **7.6 Safety**

Summaries of safety will be based on all treated subjects by treatment arm, except for the resource utilization (based on all randomized subjects).

### **7.6.1 Adverse Events**

#### **Adverse Events, Serious Adverse Events**

The following summary tables of AEs and SAEs will be restricted to events occurring in the on-study phase (see [Section 4.3.1.1](#)).

- On-study phase AEs (worst CTC grade [Any grade, 3-4, 5] of any event and of events by SOC)
- On-study phase AEs (worst CTC grade [1, 2, 3, 4, 5, unknown, any grade] of any event and of events by SOC)
- On-study non-serious AEs occurring in at least 5% of subjects (worst CTC grade [Any grade, 3-4, 5] of any event and of events by SOC)
- On-study phase SAEs (worst CTC grade [Any grade, 3-4, 5] of any event and of events by SOC)
- On-study phase SAEs (worst CTC grade [1, 2, 3, 4, 5, unknown, any grade] of any event and of events by SOC)
- On-study phase drug-related AEs (worst CTC grade [Any grade, 3-4, 5] of any event and of events by SOC)
- On-study phase drug-related AEs (worst CTC grade [1, 2, 3, 4, 5, unknown, any grade] of any event and of events by SOC)
- On-study phase drug-related SAEs (worst CTC grade [Any grade, 3-4, 5] of any event and of events by SOC)
- On-study phase drug-related SAEs (worst CTC grade [1, 2, 3, 4, 5, unknown, any grade] of any event and of events by SOC)

- On-study phase AEs leading to discontinuation of ipilimumab (worst CTC grade [Any grade, 3-4, 5] of any event and of events by SOC)
- On-study phase AEs leading to discontinuation of ipilimumab (worst CTC grade [1, 2, 3, 4, 5, unknown, any grade] of any event and of events by SOC)

Listings by subject will be produced for all AEs (including drug-related AEs and those leading to discontinuation of ipilimumab), all AEs leading to discontinuation of ipilimumab (including drug-related AEs), all SAEs (including drug-related SAEs).

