## 6.3 Populations for Analyses

The statistical analyses in this study will be defined with respect to the following data sets.

**All Enrolled Subjects:** All subjects who signed an informed consent form and were registered into the IVRS. Subject disposition will be based on all enrolled subjects.

**All Randomized Subjects:** All enrolled subjects who were randomized to a treatment arm (ipilimumab or DTIC). Unless otherwise indicated, analyses of most of study population and efficacy endpoints will be based on all randomized subjects and will be performed using the treatment group as randomized (i.e. on an intent-to-treat basis). Analyses of QoL will also be based on the all randomized subjects population: subjects with both baseline and on-study measurements will contribute to the analyses of change at on-study time-points.

**Response Evaluable Subjects:** All randomized subjects who have measurable disease (i.e., at least one measurable lesion) at baseline.

**All Treated Subjects:** All subjects who received at least one dose of treatment with ipilimumab or DTIC. Unless otherwise specified, analyses of safety and extent of exposure will be based on

all treated subjects. Analyses of all treated subjects will be performed using the treatment group as treated.

**Pharmacokinetic Subjects:** All available pharmacokinetic data from subjects who received ipilimumab will be included.

**ADA Evaluable Subjects:** All treated subjects with baseline and at least one post-baseline ipilimumab immunogenicity assessment

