## 7 STATISTICAL ANALYSES

### 7.1 General Methods

No interim analyses are planned for this study. The final analysis will be performed when a minimum of 2 year follow-up is reached by all randomized subjects.

Unless otherwise noted, the bulleted titles in the following subsections describe tabulations of discrete variables, by the frequency and proportion of subjects falling into each category, grouped by treatment (with total). Percentages given in these tables will be rounded to the first decimal and, therefore, may not always sum to 100%. Percentages less than 0.1 will be indicated as ‘< 0.1’. Continuous variables will be summarized by treatment group (with total) using the mean, standard deviation, median, minimum and maximum values. Subject listings will be produced to accompany the tabulations. Time-to-event variables (e.g. time-to resolution) will be analyzed using the Kaplan-Meier technique. When specified, the median will be reported along with 80% CI using Brookmeyer and Crowley method (using log-log transformation for constructing the confidence intervals). The conventions to be used for imputing partial dates for analyses requiring dates are described in [Section 8](#).

Frequency tables of subject characteristics and subset analyses of efficacy endpoints (including those by M-substage and BRAF mutation status) will be based on the assessment recorded on the baseline CRF. However, stratified analyses will be based on the variables used by the IVRS to randomize the subject.

Assessments taken during re-induction and subsequent progression follow-up phase will not contribute to derived endpoints, such as BOR or PFS, since these assessments are necessarily following an initial progression. However exploratory version of these endpoints corresponding to the administration of re-induction therapy may be performed (if there are sufficient data) - details will be provided in the DPP.

All statistical analyses will be carried out using SAS software (SAS Institute, Cary, North Carolina, USA), unless otherwise noted.

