### **7.4.2      *Discontinuation from Induction Phase***

Failure to complete the (re-)induction phase will be tabulated.

- Number of subjects who completed or failed to complete (with reason) the (re-)induction phase.

- Discontinuation from study therapy in induction phase (subjects with study therapy discontinued, reason for discontinuation).
- Discontinuation from ipilimumab in re-induction phase (subjects with study therapy discontinued, reason for discontinuation).

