#### **7.4.3      *Interruption of Infusion or Delay of Study Therapy***

An infusion interruption refers to an interruption of the infusion of study therapy, whether or not the infusion is resumed. A dose delay refers to a delay in the administration of ipilimumab (but not a discontinuation thereof) relative to the protocol schedule. A dose omission refers to an omission in the administration of DTIC (but not a discontinuation thereof) relative to the protocol schedule.

- Infusion interruption in induction phase (subjects with at least one interrupted dose, reason for first dose interruption, number of interruptions).
- Infusion rate reduction in induction phase (subjects with at least one infusion with IV rate reduced, reason for first infusion IV rate reduced, number of infusions with IV rate reduced).
- Dose delay of ipilimumab in induction phase (subjects with at least one delayed dose, reason for first dose delay, number of delays).
- Dose omission of DTIC in induction phase (subjects with at least one omitted dose, reason for first dose omitted, number of omissions).
- Infusion interruption of ipilimumab in re-induction phase (subjects with at least one interrupted dose, reason for first dose interruption, number of interruptions).
- Infusion rate reduction of ipilimumab in re-induction phase (subjects with at least one infusion with IV rate reduced, reason for first infusion IV rate reduced, number of infusions with IV rate reduced).
- Dose delay of ipilimumab in re-induction phase (subjects with at least one delayed dose, reason for first dose delay, number of delays).

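### SAP 7.6.1 filters its tables and dedicated listing of AEs leading to discontinuation on ipilimumab, so as worded they give no DTIC counterpart by SOC and grade

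*SAP*

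**What the plan says.** SAP 7.6 sets the general rule: "Summaries of safety will be based on all treated subjects by treatment arm". The only exception it states is resource utilization. SAP 6.3 defines the treated population as "All subjects who received at least one dose of treatment with ipilimumab or DTIC".

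SAP 7.6.1 then lists the AE and SAE summary tables. Most name no drug. The two on discontinuation are both headed "On-study phase AEs leading to discontinuation of ipilimumab"; they differ only in how the grades are grouped. Of the by-subject listings, one is dedicated to discontinuation: "all AEs leading to discontinuation of ipilimumab (including drug-related AEs". The general listing covers "all AEs (including drug-related AEs and those leading to discontinuation of ipilimumab".

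Other parts of the SAP bear on stopping treatment:

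- SAP 7.4.2 plans "Discontinuation from study therapy in induction phase (subjects with study therapy discontinued, reason for discontinuation". A separate item there covers ipilimumab in re-induction.
- SAP 7.1 adds that "Subject listings will be produced to accompany the tabulations".
- The imAR part of SAP 7.6.1 plans a table of imARs that led to stopping study drug, split by high-dose corticosteroid use and subcategory.

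**The concern.** A subject treated only with DTIC cannot discontinue ipilimumab. A table with a column for each arm, but with events selected by whether ipilimumab was stopped, therefore shows nothing under DTIC whatever happened in that arm. A reader could take the blank or zero to mean that no AE led to stopping DTIC.

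At stake is one element of the tolerability comparison in a randomized, open-label trial. Protocol 1.5 itself describes DTIC as having significant toxicities, so which events stopped each treatment, and how severe they were, is of interest in both arms. No hypothesis test, endpoint, analysis population or error rate is involved.

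**Working it through.** The plan states no figure to reproduce. The check is a reading of the visible outputs against the SAP's own population rule, plus simple counts.

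**Step 1: summary tables in the AE and SAE part of SAP 7.6.1.**

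| Subject of table | Tables | Drug named |
|---|---|---|
| All AEs | 2 | none |
| Non-serious AEs | 1 | none |
| SAEs | 2 | none |
| Drug-related AEs | 2 | none |
| Drug-related SAEs | 2 | none |
| AEs leading to discontinuation | 2 | ipilimumab |

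Tables naming no drug: 2 + 1 + 2 + 2 + 2 = 9. Total: 9 + 2 = 11. So 2 of 11 are limited, and they are the only two on discontinuation.

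**Step 2: by-subject listings in the same part.** There are three: all AEs, AEs leading to discontinuation, and all SAEs. Only the second is limited to ipilimumab, so 1 of 3. The all-AE listing mentions ipilimumab discontinuation inside an inclusive parenthesis, which does not narrow it.

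**Step 3: population against event filter.** Under SAP 7.6 and 6.3, DTIC-treated subjects belong in both tables and have their own column. The event filter then removes every event in that column. The one exception is a dosing error: under SAP 6.2, a subject wrongly given ipilimumab for only part of treatment stays in the DTIC group.

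**Step 4: does another visible output fill the gap?**

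| Output | Covers DTIC? | By SOC and worst grade? |
|---|---|---|
| SAP 7.4.2, induction discontinuation by reason | yes | no |
| SAP 7.1, accompanying listings | yes | no, subject-level only |
| SAP 7.6.1, all-AE listing | yes | no, subject-level only |
| SAP 7.6.1, imARs leading to stopping study drug | no single drug named | no; imARs only, by subcategory |

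Visible outputs summarising AEs that led to DTIC discontinuation by SOC and worst grade: 0.

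**Step 5: is the restriction deliberate?** The evidence leans towards a slip.

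- SAP 7.4.2 uses the neutral term for induction and names ipilimumab only for re-induction, where it is the only drug given. The two tables in question are not confined to re-induction.
- The imAR table uses neutral wording.
- SAP 7.4.3 pairs its ipilimumab dose-delay table with "Dose omission of DTIC in induction phase".
- Some imAR listings carry an explicit instruction to present only regimens containing ipilimumab. The AE tables carry none.

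Against this, SAP 7.4.1 plans the time from randomization to first dose for ipilimumab alone, so the SAP is not consistently two-sided.

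**Step 6: size of the arm.** SAP 2.1 plans about 180 subjects at 2:1, so DTIC is 180 / 3 = 60. The documents give no rate of AE-related DTIC discontinuation, so the number of affected subjects cannot be stated.

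**The case against.** The strongest reply is that the by-arm rule in SAP 7.6 already governs, that the ipilimumab wording is an evident slip a programmer would correct, and that SAP 9 leaves the list of outputs to the Data Presentation Plan. That plan was not available, nor was the text of SAP 4.3.1.1, which 7.6.1 cites for the on-study phase. Either may define these outputs for both drugs. This stands as a limit: the point concerns the visible SAP wording and does not show a gap in what was reported. It does not remove the point, because the by-arm rule fixes the columns while the table wording fixes which events are counted.

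It is also fair to say that much of the information is planned already. DTIC AEs, SAEs and drug-related events appear by SOC and grade in the other nine tables, and stopping is tabulated by reason. What is missing is one cross-classification.

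Three stronger readings are tempting, and the documents do not support them:

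- That DTIC discontinuations go unreported. SAP 7.4.2 and the all-AE listing cover them in part.
- That DTIC subjects are excluded from the two tables. They are in the population and the layout; only the event filter shuts out their events.
- That the all-AE listing is also restricted. Its parenthesis is inclusive, so every DTIC AE is listed.

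**Conclusion.** The point holds as a defect of wording in the safety section. Both discontinuation-AE tables and the dedicated listing select on ipilimumab, in conflict with the SAP's own by-arm rule. As written, the plan yields no comparison between arms of AEs leading to discontinuation by SOC and worst grade.

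The conclusion assumes that the visible text is followed literally and that neither the Data Presentation Plan nor SAP 4.3.1.1 broadens these outputs. A slip is the more likely explanation but is not proven. The priority is low, since the primary and secondary efficacy analyses are untouched.

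**What to change.** In the two tables and the dedicated listing, refer to discontinuation of *study therapy* in place of ipilimumab, and present them by arm as treated. Make the same change in the parenthesis of the all-AE listing for consistency. If the Data Presentation Plan or SAP 4.3.1.1 already covers DTIC, align the SAP wording with it. If the restriction was intended, the SAP should say so and give the reason.

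The cost is low. If the outputs have not been produced, only SAP text and table shells change. Protocol 1.2 gives the database lock as 03Jun2019, so if they were produced after that date, two corrected tables and one listing can be added to the study report from existing data. Both routes depend on the CRF having recorded action taken with DTIC. The documents do not show this, so it should be checked first.
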